### 6.3. Inclusion of Women and Minorities

Both men and women of all races and ethnic groups are eligible for this trial.

**Table 2. Inclusion of Women and Minorities**

Ethnic Category	Accrual Targets			Total
	Females		Males	
Hispanic or Latino	4	+	4	8
Not Hispanic or Latino	11	+	12	23
Ethnic Category: Total of all subjects	15	+	16	31
Racial Category				
Asian	2	+	2	4
Black or African American	2	+	2	4
White	11	+	12	23
Racial Category: Total of all subjects	15	+	16	31

### 6.4. Subject Recruitment

This study will be conducted at Columbia University Medical Center. Thirty-one patients will be needed to meet the primary study endpoint. The amount of time required to complete this trial will depend on the rapidity of accrual. We estimate evaluation of 3-5 subjects a month in our center with enrollment of 2 subjects a month to complete accrual over 16-18 months with an anticipated 4-6 week pause after enrolling the 6th subject for safety analysis. If the first dose level is deemed intolerable ( $\geq 2$  DLTs), we will accrue 6 subjects at a lower dose level and complete 31 subjects (25 additional) at that dose level. Thus the maximum number of subjects enrolled in this study will be 37.

Participation is voluntary. The patient must be aware of the neoplastic nature of his/her disease and willingly consent after being informed of the procedures to be followed, the

experimental nature of the therapy, alternatives, potential benefits, side effects, risks, and discomforts. The investigator will make certain that an appropriate informed consent process is in place to ensure that potential research subjects, or their authorized representatives, are fully informed about the nature and objectives of the clinical study, the potential risks and benefits of study participation and their rights as research subjects.

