### 1.1. Trial Design Overview

This is a single-arm, single-center, open-label trial of azacitidine combined with pembrolizumab in subjects with locally-advanced or metastatic pancreatic adenocarcinoma. Thirty-one evaluable subjects will be enrolled to assess the efficacy and safety of combination therapy in the second- line setting.

All subjects will have received systemic first-line chemotherapy, 5-FU or gemcitabine-based combination or monotherapy, prior to enrollment on the study. Azacitidine daily for 5 days will be given every 4 weeks (28 days). Fixed-dose pembrolizumab will be administered every 3 weeks for up to approximately 2 years beginning 2 weeks after initiation of azacitidine. The primary efficacy endpoint will be progression-free survival among all enrolled subjects. Disease progression will be determined based on RECIST 1.1 criteria; however, patients will be permitted to continue therapy following the development of progression of disease by RECIST 1.1 criteria if considered clinically appropriate by the study principal investigator.

As preliminary data suggests there is minimal toxicity overlap between pembrolizumab and a hypomethylating agent, there will be an accelerated Phase 1 dose determination component of the study. In the initial cohort, low-dose azacitidine will be administered, as studied in patients with advanced or metastatic solid tumors, and pembrolizumab will be administered at fixed dose

as detailed in the protocol. An initial cohort of 6 subjects will be enrolled, treated with combination therapy, and assessed for safety. Following enrollment of the initial 6 evaluable subjects all toxicity data will be reviewed. If 2 or more patients experience a treatment related dose-limiting toxicity (DLT) within the first 6 weeks of treatment administration (Defined in Section 5.2), then accrual at that dose level will stop. We will allow for 1 dose reduction in azacitidine and if agreed by the PI, the study will resume at the lower dose (Dose -1) and will again accrue 6 subjects who will receive combination therapy. If 2 or more subjects experience treatment related DLTs at this level, we will discontinue the combination study.

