## 5.2. Dose Limiting Toxicities

All toxicities will be graded according to the NCI CTCAE version 4.0 and assessed for relationship to study medications.

The incidence of DLT(s) assessed in the first 6 evaluable subjects during the first 6 weeks will be to initially determine whether the dose level of combination therapy is tolerable. A subject will be considered evaluable for DLT if they have received at least 1 dose of pembrolizumab after receiving the initial week of azacitidine. DLT should not be an AE considered by the investigator to be disease related. The following drug-related AE (whether related to one or both agents) will be considered a DLT:

- Any Grade  $\geq 3$  drug-related non-hematological AE, including the following laboratory abnormalities
  - If a subject has baseline Grade  $\leq 1$  AST, ALT, or total bilirubin, a drug-related Grade  $\geq 3$  toxicity will be considered a DLT
  - If a subject has baseline asymptomatic Grade 2 AST or ALT due to tumor infiltration in the liver, drug-related elevations in AST and/or ALT  $> 2x$  baseline or a maximum of  $> 8x$  ULN that does not resolve to Grade 2 or less within 48 hours (if symptomatic) or that does not resolve to Grade 1 or less within 3 weeks of onset (if asymptomatic) will be considered a DLT.
- Any Grade  $\geq 3$  drug-related non-hematological laboratory abnormality with the following exceptions:
  - Grade 3 abnormal laboratory result that is asymptomatic and lasts no longer than 72 hours.
  - Grade 4 lymphocytopenia not associated with symptoms or clinical manifestations
- Any toxicity managed by discontinuation of pembrolizumab (see [section 9.1](#)).
- Any toxicity managed by discontinuation of azacitidine (see [section 9.2](#)).
- Grade  $\geq 3$  thrombocytopenia with bleeding, and febrile neutropenia of any Grade.

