Serum CA 19-9 e,h	X			X		X		X		X then Q6W		X			
HBV, HCV, HIV c,i	X														
Efficacy Measurements															
Tumor Imaging	X j						X k then Q8W					X l			
Tumor Biopsies/Archival Tissue Collection/Correlative Studies Blood															
Archival or Newly Obtained Tissue Collection m	X						X					X optional			
Correlative Studies Blood Collection	X n			X	X	X						X			

a. Unless otherwise specified, assessment/procedures are to be performed prior to dose administration on Day 1 of each cycle.

b. Subjects who discontinue study treatment without documented disease progression should continue to be monitored for disease by radiologic imaging every 8 weeks (□7 days) until (1) the start of new anti-cancer treatment, (2) disease progression, (3) death, or (4) the end of the study, whichever occurs first.

c. Informed consent will include consent for correlative studies including biopsies and serum collections.

d. For women of reproductive potential, a negative pregnancy test should be performed within 72 hours prior to first dose of trial treatment. Pregnancy tests (serum and/or urine tests) should be repeated if required by local guidelines.

e. Laboratory Screening Tests should be performed within 7 days prior to first dose of treatment. For all subjects, unresolved abnormal labs resulting in drug-related AEs should be followed until resolution. Post dose lab may be collected up to 72 hours prior to the scheduled timepoint.

f. Chemistry will be collected on Day 1 of each cycle of azacitidine and pembrolizumab.

g. CBC with differentials will be collected on Day 1 of each cycle of azacitidine and pembrolizumab.

h. On treatment CA 19-9 – starting at Cycle 1 of Pembrolizumab, CA 19-9 will be collected Q3W until week 15 then every 2 pembrolizumab cycles (Q6W +/- 2 weeks) through the end of treatment

i. All subjects will be tested for HIV, HBV, and HCV prior to enrollment. Those who are positive for HIV, untreated active Hepatitis B, and dual infection with HBV/HCV will be excluded.

j. Tumor imaging at screening: Imaging will be performed within 28 days prior to the first dose of induction. Imaging should include CT chest, abdomen, and pelvis or MRI if CT is clinically contraindicated.

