### **15.2. Populations for Statistical Analysis and Reporting**

#### **15.2.1 DLT Evaluable Population**

The DLT Evaluable Population consists of subjects in the initial 6 patient DLT cohort who complete at least 5 doses of azacitidine and 1 dose of pembrolizumab and completed the DLT observation period (6 weeks), and those who did not complete the DLT observation period and discontinued from study treatment due to a DLT event. The DLT Evaluable Population will be used for DLT assessments.

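### The 4-6 week accrual pause is counted from the sixth subject's enrolment and does not secure the 6-week DLT window; the protocol's definitions of DLT-evaluable conflict on when the safety gate may be read

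*Combined protocol and SAP*

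**What the plan says.** **The pause.** Section 6.4 estimates 2 enrolments a month and 16-18 months of accrual, "with an anticipated 4-6 week pause after enrolling the 6"th subject.

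**The review.** Section 1.1 states: "Following enrollment of the initial 6 evaluable subjects all toxicity data will be reviewed". The gate is two or more DLTs "within the first 6 weeks of treatment administration"; with at most one, 25 more subjects are treated.

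**The window.** Section 5.2 also uses 6 weeks: "The incidence of DLT(s) assessed in the first 6 evaluable subjects during the first 6 weeks". Section 15.2.1 builds the DLT Evaluable Population from subjects who had the required doses and "completed the DLT observation period (6 weeks), and those who did not complete the DLT observation period" because they stopped for a DLT.

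**Who is evaluable.** Section 5.2 calls a subject "evaluable for DLT if they have received at least 1 dose of pembrolizumab" following the initial azacitidine week. Section 13.1.1 similarly asks for five azacitidine doses and one pembrolizumab dose. Neither mentions completing 6 weeks.

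**The assessments.** In the Section 12.1 flow chart, adverse-event review, physical examination, CBC and chemistry fall at weeks 3, 5, 6 and then 9, before dosing. Footnote f reads: "Chemistry will be collected on Day 1 of each cycle of azacitidine and pembrolizumab". Week 8 has tumour imaging and a biopsy, but none of those four.

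**The concern.** The six-subject gate is the only safety rule in the protocol with a numeric threshold; Section 13.8 gives none. It decides whether 25 more subjects receive the combination. No section says that accrual stays closed until the sixth subject has completed the window. The pause and the review are both tied to enrolment, and under Section 7.1 enrolment must come before the first dose. Section 15.2.1 would prevent an early count, but Sections 5.2 and 13.1.1 would not.

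The scheduled safety data add to the problem. The last in-window set is taken before the second pembrolizumab dose, so the final days of the window have no routine assessment until week 9. One liver-enzyme DLT item in Section 5.2 also depends on whether an elevation resolves within 3 weeks of onset, so an onset on day 36 cannot be classified until day 57 (36 + 21).

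Both gaps act in one direction: they can lower the number of DLTs counted, and so favour declaring the dose safe.

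**Working it through.** **Inputs.** Pause of 4-6 weeks and 2 enrolments a month (Section 6.4); 6-week window (Sections 1.1, 5.2, 15.2.1); gate of 2 or more of 6 (Section 1.1); pembrolizumab every 21 days from week 3 (Table 3); azacitidine every 28 days; visit weeks from Section 12.1. Assumptions: the window runs from the first azacitidine dose, accrual is even, dosing starts on the enrolment day unless stated, and a month is 365.25/12 = 30.44 days.

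**1. The plan's own accrual figure.** Months = 31/2 + pause.
- 4 weeks: 15.5 + 28/30.44 = 16.4
- 6 weeks: 15.5 + 42/30.44 = 16.9

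Both lie within the stated 16-18 months.

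**2. Calendar.** Day 1 of week w = 7(w - 1) + 1. Week 3 is day 15, week 5 is day 29, week 6 is day 36, week 8 is day 50 and week 9 is day 57 (nominal days; visits have a ±3 day window). The DLT window ends on day 42.

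**3. Pause against window for the sixth subject.**
- Low end: at most 28 days, or 28/42 = 67% of the window. This is before the second azacitidine course (day 29) and the second pembrolizumab dose (day 36).
- High end: 42 days only with same-day dosing. Otherwise it falls short by the enrolment-to-dose lag, which is not stated; a 7-day lag, for illustration, leaves 35 of 42 days. A replacement subject would need a fresh window.
- If the 6 weeks were counted from the first pembrolizumab dose, the window would end on day 56 (14 + 42), and both ends would fall short.

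**4. Schedule against window.** Day 42 is 6 days after the week-6 assessments and 15 days before the week-9 assessments.

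**5. Who is affected when the pause ends.** At 2 a month, subjects are 30.44/2 = 15.2 days apart.
- After 4 weeks: subject 6 is at 28 days, subject 5 at about 43 and subject 4 at about 58. Subjects 1-4 have reached week 9; subjects 5 and 6 have not.
- After 6 weeks: subject 5 is at about 57 days, so only subject 6 has not clearly reached week 9.
- At 3 a month, the upper rate in Section 15.4, a 4-week pause also cuts subject 5 to about 38 days.

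**6. Effect on the gate.** With full follow-up, P(2 or more of 6) = 1 - (1-p)^6 - 6p(1-p)^5. At p = 0.30 this is 1 - 0.1176 - 0.3025 = 0.580.

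If DLT onset is uniform over the 42 days, the sixth subject's observed rate is 0.30 × 28/42 = 0.20. For the other five, P(0) = 0.1681 and P(1) = 0.3602. Then P(2 or more) = 1 - 0.1681 - 0.3602 × 0.80 = 0.544.

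| True DLT rate | Full window | Sixth subject at 28/42 |
|---|---|---|
| 0.20 | 0.345 | 0.317 |
| 0.30 | 0.580 | 0.544 |
| 0.33 | 0.642 | 0.606 |
| 0.40 | 0.767 | 0.732 |

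If onset is instead uniform over days 15-42 only, the sixth subject's observed rate is 0.30 × 14/28 = 0.15, and the result is 1 - 0.1681 - 0.3602 × 0.85 = 0.526.

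**7. Upper bound.** Keep uniform onset over days 15-42, and suppose every event in the last 7 of those 28 days is missed in all six subjects. The observed rate is then 0.30 × 0.75 = 0.225, and P(2 or more) = 1 - 0.2167 - 0.3774 = 0.406. If subjects 1-4 are credited with their week-9 data, and subjects 5 and 6 are set at 0.225 and 0.15, the result is about 0.50.

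**The case against.** Section 6.4 is an accrual forecast, not the gate. Its range reaches 6 weeks, and Section 15.2.1, if applied, keeps a DLT-free subject at day 28 out of the count. That is fair, and a reader should not infer that the gate will be read early. What stands is that Sections 5.2 and 13.1.1 define evaluability differently and no text decides between them.

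A reader might also infer that subjects are not seen at all between day 36 and day 57, or that none of the six has a scheduled assessment after the second pembrolizumab dose when the gate is read. The documents support neither. Week 8 brings imaging and a biopsy, and at 2 a month subjects 1-4 have passed week 9 even after a 4-week pause.

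Nor is a late finding necessarily impossible to date. Adverse events are reportable throughout treatment (Section 10.6), start and stop dates are recorded (Table 7), and extra assessments are allowed (Section 12.1.6.1). Serious events go to the DSMC within 24 hours, and it meets twice a month. What remains exposed is mainly persistent, asymptomatic laboratory abnormality.

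**Conclusion.** The point holds as a conflict between sections with a modest effect. The low end of the pause leaves a third of the sixth subject's window unobserved, the high end has no margin, and the definitions of evaluable do not settle when the gate may be read.

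The pause alone costs about 3-4 points of stopping probability at true DLT rates of 20-40%, assuming uniform onset and one truncated subject. A fall from 58% to 41% is tempting to cite, but it is a bound that requires every day 36-42 event to be missed in all six subjects. The assessment gap mainly concerns subjects 5 and 6.

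This is a should-fix: the effect is small, but it leans towards declaring the dose safe and the correction is cheap.

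**What to change.** 1. In Sections 6.4 and 1.1, replace the 4-6 week pause with a statement that accrual does not resume until the sixth DLT-evaluable subject, after any replacement, has completed the protocol's own 6-week window and the toxicity review is done.
2. Reconcile the evaluability definitions in Sections 5.2 and 13.1.1 with Section 15.2.1, so that the term in item 1 has one meaning.
3. Reconcile the Section 12.1 schedule with the window, for example by having the already scheduled week-9 data available at the review. Neither the DLT window nor the rule for what counts as a DLT needs to change.

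**Cost.** The pause becomes about 6 weeks plus the enrolment-to-dose lag, or about 8-9 weeks if week-9 data are awaited. At 2 a month, 31 subjects take 16.9 months plus the lag, or 15.5 + 56/30.44 = 17.3 to 15.5 + 63/30.44 = 17.6 months, within the stated 18 (replacements would add time). The 37-subject path with two pauses already exceeds 18 months at that rate as planned: 18.5 + 2 × 0.92 = 20.3 to 18.5 + 2 × 1.38 = 21.3 months. No visit or test is added.

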## **6.5. Early Withdrawal of Subjects**

When a subject discontinues/withdraws prior to trial completion, all applicable activities scheduled for the final trial visit should be performed at the time of discontinuation. Any adverse events which are present at the time of discontinuation/withdrawal should be followed in accordance with the safety requirements outlined in Section 10.6 - Assessing and Recording Adverse Events. Subjects who discontinue for toxicity but do not withdraw consent from the study will continue to be followed for post-study treatment and survival as described. Subjects who a) attain a CR or b) complete 24 months of treatment with pembrolizumab may discontinue treatment with the option of restarting treatment in the future after consultation with the sponsor. After discontinuing treatment following assessment of CR, these subjects should return to the site for a Safety Follow-up Visit (described in Section 6.6.1 and then proceed to the Follow-Up Period of the study (described in Section 6.6.2).

### **6.5.1 When and How to Withdraw Subjects**

Subjects may withdraw consent at any time for any reason or be dropped from the trial at the discretion of the investigator should any untoward effect occur. In addition, a subject may be withdrawn by the investigator or the Sponsor if enrollment into the trial is inappropriate, the trial plan is violated, or for administrative and/or other safety reasons.

A subject must be discontinued from the trial for any of the following reasons:

- The subject or legal representative withdraws consent.
- Confirmed radiographic disease progression
  - *Note:* A subject may be granted an exception to continue on treatment with confirmed radiographic progression if clinically stable or clinically improved.
- Unacceptable adverse experiences
- Intercurrent illness that prevents further administration of treatment
- Investigator's decision to withdraw the subject
- The subject has a confirmed positive serum pregnancy test
- Noncompliance with trial treatment or procedure requirements
- The subject is lost to follow-up
- Completed 24 months of uninterrupted treatment with pembrolizumab or 35 administrations of study medication, whichever is later.
  - *Note:* 24 months of study medication is calculated from the date of first dose. Subjects who stop pembrolizumab after 24 months may be eligible for up to one year of additional study treatment if they progress after stopping study treatment after consultation with the sponsor.

- Administrative reasons

### **6.5.2 Data Collection and Follow-up for Withdrawn Subjects**

The End of Treatment and Follow-up visit procedures are listed in Section 12.1 (Trial Flow Chart) and Section 12.3 (Administrative Procedures). After the end of treatment, each subject will be followed for 30 days for adverse event monitoring (serious adverse events will be collected for 90 days after the end of treatment as described in Section 10). Subjects who discontinue for reasons other than progressive disease will have post-treatment follow-up for disease status until disease progression, initiating a non-study cancer treatment, withdrawing consent or becoming lost to follow-up. After documented disease progression each subject will be followed by telephone for overall survival until death, withdrawal of consent, or the end of the study, whichever occurs first.

## **6.6. Post-Treatment Visits**

### **6.6.1 Safety Follow-Up Visits**

The mandatory Safety Follow-up Visit should be conducted approximately 30 days after the last dose of trial treatment or before the initiation of a new anti-cancer treatment, whichever comes first.

All AEs that occur prior to the Safety Follow-Up Visit should be recorded. Subjects with an AE of Grade >1 will be followed until the resolution of the AE to Grade 0-1 or until the beginning of a new anti-cancer therapy, whichever occurs first. SAEs that occur within 90 days of the end of treatment or before initiation of a new anti-cancer treatment should also be followed and recorded.

Subjects who are eligible for retreatment with pembrolizumab may have up to two safety follow-up visits, one after the Initial Treatment Period and one after the Second Course Treatment Phase.

### **6.6.2 Follow-Up Visits**

Subjects who discontinue trial treatment for reasons other than disease progression will move into the Follow-up Phase and should be assessed Q8W by radiologic imaging to monitor disease status. Every effort should be made to collect information regarding disease status until the start of a new anti-cancer therapy, disease progression, death, or the end of the study.

Information regarding post-study anti-cancer treatment will be collected if new treatment is initiated.

### **6.6.3 Survival Follow-Up**

Subjects, who experience disease progression (by site assessment) or start a new anti-cancer therapy, will move into the Survival Follow-Up Phase. Subjects should be contacted (e.g., by telephone or visit) every 12 weeks to assess for survival status until death, withdrawal of consent, or the end of the study, whichever occurs first Post-study anti-cancer therapy will be collected during survival follow-up.

## 7. REGISTRATION PROCEDURES

### 7.1. CUMC Research Participant Registration

Confirm eligibility as defined in the section entitled Criteria for Subject Eligibility.

Obtain informed consent, by following procedures defined in section entitled Informed Consent Procedures, along with applicable institutional policies and federal regulations.

Only Investigators/Research personnel properly trained and delegated to consent subjects for this protocol will participate in the consenting process. Furthermore, properly delegated/trained Physician Investigators (e.g., MD, MD PhD) are required to sign/verify a protocol specific Eligibility Checklist for each subject enrolled on the study, in addition to providing the relevant source documentation confirmation subject eligibility.

All participants must be centrally registered through the Central Registration Office within Herbert Irving Comprehensive Cancer Center at CUMC prior to initiation of study treatment. Registration hours are available Monday through Friday from 9:00am – 5:00pm EST (excluding holidays and weekends). Same day patient registrations (and after hour registrations) will be accommodated on a case by case basis provided that the study team has expressed all time sensitive registration concerns/cases in a timely manner to the Central Registration Office.

